9.1.3 Handling of Specimens

- Slides are to be labeled with the patient PBTC Accession # and these slides should be designated as PBTCRB # (where the # assigned from 1 to 20, or the highest number of unstained sections prepared, sequentially) or PBTCCRB H&E for the H&E stained section. The tubes containing scrolls are to be labeled with the PBTC Accession # and the PBTC study for which the sample is provided.
- Scrolls of Formalin Fixed, Paraffin Embedded (FFPE) tumor materials are to be labeled with the PBTC Accession # and the PBTC study for which the sample is provided. Scrolls of FFPE tumor material should be shipped at room temperature.
- PBMCs are to be labeled with the PBTC Accession # and the PBTC study for which the sample is provided. Samples should be shipped overnight in a separate box with a 2-day supply of dry ice.

9.1.4 Shipment of Specimens

Samples collected for distribution and storage in the repository should be sent to the PBTC CRB via FedEx by completing the Internet form at http://www.fedex.com/us/ and using the cc function to email PBTC CRB, the repository contact. FedEx user ID and password for pathology shipping can be found at PBTC-039 protocol. Samples are to be shipped to:

PBTC CRB Research Support and Biorepository Services Children's Hospital Los Angeles

9.1.5 Assessment of WNT and MAPK Pathway Activation

FFPE tissue is obtained for diagnostic purposes in virtually all brain tumor resections, unlike frozen tumor material, which is obtained at the discretion of the neurosurgeon. Tumor material submission is optional but strongly encouraged for exploration for evidence of WNT pathway activation by immunohistochemistry (IHC) for nuclear beta-catenin protein and MAPK pathway activation by pyrosequencing for BRAF V600E mutation in tumor tissue. Investigators should make every effort possible to obtain tissue when available and must review with the study chair or co-chair if tissue is not available.

• WNT Pathway Activation IHC:

FFPE tumor sections will be evaluated for evidence of WNT pathway activation through staining for nuclear and cytoplasmic beta-catenin expression (phospho- β catenin, β -catenin supplied by New England Biolabs, Beverly, MA). The assays have been developed and validated previously on medulloblastoma samples. ³³

• Detection of BRAF V600E mutation by pyrosequencing

FFPE tumor sections will be evaluated for evidence of MAPK pathway activation through detection of the BRAF V600E mutation by pyrosequencing, using protocols currently in use in the Molecular Neuropathology laboratory, Department of Pathology, Texas Children's Hospital.

9.1.6 Collection of Specimen(s)

- Twenty slides (5-6 µm) of unstained FFPE tissue are requested for IHC of WNT pathway to evaluate evidence of WNT pathway activation in resected tumor tissue. The referring pathology departments should cut and send slides to the PBTC-CRB see Section 9.1.4.
- Scrolls should be cut $(3 \times 20 \ \mu m)$ into 1.5ml microfuge tubes. Tubes should be labeled with the patient's PBTC Accession number.

9.1.7 Site Performing Correlative Study

Analysis will be performed by [name], PhD, in the Department of Pathology Texas Children's Hospital/Baylor College of Medicine.

9.2 Central Pathology Review

Central pathology review is required for this study. Pathologist review for this study will include the following elements:

- For each subject one H&E stained slide per one representative block from the brain tumor, removed either at initial diagnosis or relapse, should be submitted for review.
- Review of the corresponding pathology report(s) of the immunohistochemical, special stains, and molecular/genetic results from current and/or original primary tumor
- If necessary, review of immunohistochemical or special stained slides. Slides submitted to the PBTC CRB will be digitized to 40X. H&E stained sections will be retained and

filed at the CRB. Original immunohistochemical or special stain slides will be returned to the submitting institution.

9.2.1 Pathology Central Review and Data Collection

The slides from the submitting institution will be sent to the PBTC CRB for central review. The accompanying complete pathology evaluation should be uploaded to the PBTC using the secure File Upload system. The slides will be logged into ProtoLab to document receipt of the samples. Slides will then be scanned at 40X using Leica Aperio Whole Slide Scanner. The slides will be made available for remote review by the assigned reviewer and the corresponding reports will be available via a link in ProtoLab. The reviewer will be able to access the Protolab database to enter and review results via a VPN connection accessed by assigned usernames/passwords.

9.3 Imaging Studies

9.3.1 Description of the study:

Brain MR with and without gadolinium focused on the sellar and suprasellar regions will be obtained preferably on the 3T magnet consisting of high resolution sagittal T1 images (slice thickness 3mm skip 0, 20cm FOV), high resolution coronal T1 images (slice thickness 3mm skip 0, 16 cm FOV), axial T2 images (slice thickness 2.5mm thickness skip 0, 20 cm FOV), axial T2 FLAIR images(slice thickness 4.0 mm, 20 cm FOV), high resolution coronal T2 images (slice thickness 2.0mm FOV 16cm), post gadolinium high resolution coronal T1 images (slice thickness 3mm skip 0, 16 cm FOV) and post gadolinium sagittal T1 high resolution images (slice thickness 3mm skip 0, FOV 16 cm) followed by axial T1 post-gadolinium images through the whole brain (slice thickness 4mm skip 0, FOV 20 cm).

Imaging protocol sequences will be sent to the participating sites of the PBTC. Imaging specific protocols will also be sent for 1.5T magnets with the following parameters: high resolution sagittal T1 (slice thickness 3.0mm skip 0, FOV 20 cm), axial T2 images of the whole brain (slice thickness 4.0mm skip 0, FOV 20cm), axial T2 FLAIR of whole brain(slice thickness 4.0 mm skip 0, FOV 20cm), axial T1 images of the whole brain (slice thickness 4mm skip 0, FOV 20cm), coronal FSE T2(slice thickness 3 mm, interleaved, FOV 16 cm), coronal T1 (slice thickness 3mm interleaved, FOV 16 cm), post-gadolinium high resolution coronal T1 and sagittal T1 images (3mm skip 0, FOV 16 cm).

9.3.2 Outcome Measure

See section 11 for the linear parameters used to assess response, depending on the stratum and whether the tumor is predominantly solid or cystic or both.

9.3.3 Timing of Assessment

Imaging studies will be done at baseline prior to PEGINTERFERON ALFA-2B therapy and every 12 weeks for the first 9 courses (approximately 1 year) then every 18 weeks thereafter until subjects develop evidence of disease progression, unacceptable toxicity or completion of 18 courses (approximately 2 years) of PEGINTERFERON ALFA-2B therapy.

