5.1 Agent Administration

SYLATRON will be administered as a weekly subcutaneous injection for up to 18 courses with 6 injections per course. Six consecutive weeks will constitute one course and subsequent courses will immediately follow, with no break in the administration of the drug. All patients will receive a dose of 1 mcg/kg/week. The patient's actual weight (in kilograms) should be used when calculating the dose of SYLATRON and doses should be re-adjusted if necessary at the time of each clinic evaluation. See Appendix C for the SYLATRON dosage calculation and dosage chart. Patients or parents will be taught to administer the medication in the outpatient setting (see Appendix B for a parent handout on administering subcutaneous injections). Patients or their guardians will keep a diary to document SYLATRON administration (available on the PBTC-039 webpage).

Since constitutional symptoms (e.g., fatigue, myalgias, fever) are generally the most severe after the first few doses, acetaminophen (15 mg/kg up to max dose of 1000 mg) should be given 30 minutes prior to administering the first six doses (first course) of SYLATRON and prior to subsequent doses if needed. For fever that develops after a dose of SYLATRON, Acetaminophen (15 mg/kg up to max dose of 650 mg PO) can be given q 4-6 hours as needed, but should not exceed 75 mg/kg/day for a total dose of up to 3000 mg/day. Acetaminophen can also be alternated with ibuprofen (10 mg/kg up to a max dose of 600 mg) every 6-8 hours as needed. Patients who are on replacement steroids for adrenal insufficiency should receive stress dose steroids for any fever > 101 degrees Fahrenheit (38.3 degrees Centigrade). Please see Appendix D for suggested stress steroid dosing for SYLATRON related fever.

It is recommended that a follow-up call be placed to the patient or parent within 72 hours of the first dose to evaluate for toxicities and review optimal management.

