9.3.4 Image Transfer

Only the MRI scans specified below for the two strata will be electronically transferred to the PBTC to be submitted to the PBTC Neuroimaging Center (NIC). All subject specific data will be stripped from the images and will be replaced with PBTC Accession numbers by the PBTC prior to sending images to the NIC. All image data transfer is accomplished using PGP (pretty-good-privacy) 128-bit encryption, which meets industry standard for secure communication.

Stratum I:

All imaging studies obtained during the first 9 courses of treatment (approximately 1 year) will be centrally reviewed by the NIC. In addition if they occur beyond the first 9 courses of treatment imaging studies documenting smallest disease measurement recorded since the start of protocol, responses, confirmation of responses (follow-up scan approximately 3 months later) and documenting PD will also centrally reviewed and the protocol criteria for disease assessment will be compared to the MacDonald criteria.

Stratum II:

Central review of imaging studies will be carried out only in patients with a response or progressive disease while on study. For these patients, central review of smallest disease measurement recorded since the start of protocol, imaging studies documenting responses, confirmation of responses (follow-up scan approximately 3 months later) and studies documenting PD will be carried out and the protocol criteria for disease assessment will be compared to the MacDonald criteria.

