10 STUDY CALENDAR

Table 2 Standard Clinical and Laboratory Assessments

| | Pre- Therapy | Course 1 | Course 2-9 | Course 10-18 | End of Treatment |
|--|---------------------------|----------------|----------------|---------------------------|---------------------|
| PHYSICAL ASSESSMENTS | | | | | |
| Complete History | X | | | | |
| Interval History | | X ^A | X ^C | $\mathbf{X}^{\mathbf{F}}$ | X |
| Psychiatric History** | X | X ^A | XC | $\mathbf{X}^{\mathbf{F}}$ | X |
| Performance status | X | X ^A | X ^C | $\mathbf{X}^{\mathbf{F}}$ | X |
| Physical including neurologic exam | X | X ^A | X ^C | $\mathbf{X}^{\mathbf{F}}$ | X |
| Visual field evaluation (as feasible) | X | | X ^C | $\mathbf{X}^{\mathbf{F}}$ | |
| Ophthalmology evaluation | X | | X ^C | $\mathbf{X}^{\mathbf{F}}$ | |
| Vital signs | X | X ^A | X ^C | $\mathbf{X}^{\mathbf{F}}$ | X |
| LABORATORY EVALUATION | | | | | |
| CBC (WBC, Hgb, Hct, Platelets, ANC, ALC) | X | X ^A | XC | \mathbf{X}^{F} | X |
| Serum Chemistries (Electrolytes, BUN, Creatinine, SGOT(AST), SGPT(ALT), Total Bilirubin, TSH | X | X ^A | X ^C | X ^F | X |
| Urinalysis for protein (Urine Dip) | X | X ^A | X ^C | X ^F | X |
| Serum or urine pregnancy test (for females of childbearing potential) | X | X ^C | X ^C | X ^F | |
| IMAGING EVALUATION | | | | | |
| Brain MRI with thin cuts through the sella ^D | X | | X^B | $\mathbf{X}^{\mathbf{G}}$ | X |
| OTHER | | | | | |
| Biology Studies (assessment of WNT and MAPK pathway activation) | $\mathbf{X}^{\mathbf{E}}$ | | | | |
| FFPE tumor tissue for PBTC CRB | X^{E} | | | | |
| PBMC for PBTC CRB | X^{E} | | | | |

- Assessments should be done prior to starting course 2, i.e. prior to the 7th injection.
- B Obtain every 12 weeks at time of visit and at time of progression as feasible
- C Obtain every 12 weeks at time of visit
- D See section 9.3 9.3.1
- E See section 9.1.
- F Obtain every 18 weeks at time of visit
- Obtain every 18 weeks at time of visit and at time of progression as feasible

^{*} NOTE: Patients who do not have a Brain MRI performed at or after 9 courses (approximately 12 months) will be considered failures for the purpose of assessing the primary objective according to the statistical design. See section 13.4.1.

** Psychiatric History: patient/family will be queried about mood, depression and suicidal ideations at each study visit. If there are any concerns about significant depression or any suicidal ideation, patient should be referred to Psychiatrist.

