11.1 Tumor Response Criteria

Please note, measurements are required for both the solid and cystic components

11.1.1 Complete response (CR):

Total disappearance of all radiographically detectable tumor. Response must be sustained on the follow-up scan 3 months later.

11.1.2 Partial response (PR):

At least 50% decrease in the product of the greatest perpendicular diameters of the tumor as a whole, i.e., solid and cystic components. Response must be sustained on the follow-up scan 3 months later.

11.1.3 Progressive disease (PD):

The definitions of PD vary by strata and time on treatment given that transient increases in cyst size can be seen both during interferon therapy as well as for a prolonged period of time after radiation therapy.

Stratum 1:

- o Within the first 12 months of treatment: ≥ 25% increase in the product of the greatest perpendicular diameters of the solid component AND ≥ 0.4 cm increase in each of at least two dimensions of the solid component (note that these do not have to be the same measurements used to determine the product of the greatest perpendicular diameters) compared to the smallest disease measurement recorded since the start of protocol OR any new or worsening significant neurologic/vision deficit in conjunction with a lesser change in the solid component OR any new or worsening significant neurologic/vision deficit associated with solely a change in the cystic component that does not at least stabilize following a simple cyst aspiration. Isolated cystic enlargement is not considered progressive disease during the first 12 months of treatment unless more than 1 cyst aspiration is required for symptom control.
- o After the first 12 months of treatment: ≥ 25% increase in the product of the greatest perpendicular diameters of the tumor as a whole (solid and cystic component) AND ≥ 0.4 cm increase in each of at least two dimensions of the tumor as a whole compared to the smallest disease measurement recorded since the start of protocol OR any new or worsening significant neurologic/vision deficit in conjunction with a lesser change in the tumor as a whole. If cyst aspiration is required for symptom control, the patient will be considered to have PD.

Stratum 2:

 \circ Within the first 12 months of treatment: $\geq 25\%$ increase in the product of the greatest

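### The MRI schedule does not line up with the end of course 9 (week 54), where the stratum 1 primary endpoint is read, and the plan does not say how progression first seen on a later scan counts

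*Combined protocol and SAP*

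**What the plan says.** **Course length.** Section 5.1: "Six consecutive weeks will constitute one course and subsequent courses will immediately follow, with no break in the administration of the drug".

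**Endpoint.** Sections 13.1 and 13.3 define stratum 1 success as completing nine courses, described as about one year, with neither progression nor death. The design is 28 patients with success at 18 or more, and a futility stop at 6 or fewer of the first 12. The reference rates are 50% and 75%.

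**Scans.** Section 9.3.3 places MRI at baseline and then "every 12 weeks for the first 9 courses (approximately 1 year) then every 18 weeks thereafter until subjects develop evidence of disease progression". Table 2 in Section 10 gives the same intervals. For courses 2-9 the footnote reads "Obtain every 12 weeks at time of visit and at time of progression as feasible"; for courses 10-18 it reads "Obtain every 18 weeks at time of visit and at time of progression as feasible". Table 2 shows no routine MRI in course 1, and the course 1 assessments come just before course 2.

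**Condition for success.** The note under Table 2: "Patients who do not have a Brain MRI performed at or after 9 courses (approximately 12 months) will be considered failures". Section 13.4.1 also counts patients not evaluated for the primary outcome as failures.

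**Progression rule.** Section 11.1.3 varies the definition by time on treatment because "transient increases in cyst size can be seen both during interferon therapy" and after irradiation. In stratum 1 the size criterion concerns the solid component during the first 12 months and the whole tumour afterwards. In year 1, "Isolated cystic enlargement is not considered progressive disease during the first 12 months of treatment", except where more than one aspiration is needed for symptom control.

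**The concern.** A landmark endpoint needs an assessment at the landmark, or a rule for using assessments on either side of it. Counted from baseline, the 12-week interval steps over week 54, so the first scheduled scan that can satisfy the Table 2 note comes well after the landmark. Two things then matter.

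First, the plan does not say whether progression first seen on that later scan makes the patient a failure at one year. If it does, patients are exposed to extra weeks of risk that the 75% target does not include. If it does not, the last scheduled look before the landmark is week 48, and progression between weeks 48 and 54 can be missed.

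Second, a scan at week 66 or 72 falls under the after-12-months definition. Cyst growth that was deliberately exempt in year 1 could then count against a one-year endpoint.

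The 18-of-28 success rule and the 6-of-12 futility rule both use this count, so one or two patients classified differently can change the conclusion.

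**Working it through.** **Landmark.** 9 × 6 = 54 weeks = 378 days = 12.4 months. Twelve calendar months are 52.2 weeks. Week 66 is 15.2 months and week 72 is 16.6 months.

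**Possible grids**

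| Anchor | Courses 1-9 | Afterwards |
|---|---|---|
| Baseline; 18 weeks run from the week 48 scan | 12, 24, 36, 48 | 66, 84, 102 |
| Baseline; 18 weeks run from the end of course 9 | 12, 24, 36, 48 | 72, 90, 108 |
| Week 6 visit (Table 2 only) | 18, 30, 42, 54 | 72, 90, 108 |

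Only the third reaches week 54, but its first scan is 18 weeks after the start of treatment, against the 12-week interval from baseline in 9.3.3.

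**The plan's own figures.** With stage 1 of 12 and stage 2 of 16 patients,

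P(success) = Σ over x = 7..12 of P(X₁ = x | 12, p) × P(X₂ ≥ 18 − x | 16, p).

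- p = 0.50 gives 0.081 (Section 13.3 states 0.082).
- p = 0.75 gives 0.902 (states 0.902).
- The early-stopping probabilities are 61.3% and 5.4% (states 61.6% and 5.0%). These small differences do not affect the point.

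**Moving the read.** Assume a constant hazard, 50% or 75% event-free at week 54, every patient on the baseline grid and an unchanged progression rule. Then p(t) = p₅₄^(t/54).

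*Later progression counts as failure:*

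| Read at | True 75% reads as | Power | Futility stop at true 75% | Type I error |
|---|---|---|---|---|
| Week 54 | 75.0% | 0.902 | 5.4% | 0.081 |
| Week 66 | 0.75^(66/54) = 70.4% | 0.777 | 11.2% | 0.016 |
| Week 72 | 0.75^(72/54) = 68.1% | 0.698 | 15.0% | 0.006 |

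If only half the patients are read at week 66, p = (0.750 + 0.704)/2 = 0.727 and power is 0.847.

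*Later progression does not count, and status is in effect read at week 48:* a true 50% reads as 0.50^(48/54) = 54.0% if no progression in weeks 48-54 is caught between scans.

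| Week 48-54 progression caught clinically | p | Type I error |
|---|---|---|
| None | 0.540 | 0.164 |
| Half | 0.50 + 0.5 × 0.040 = 0.520 | 0.118 |
| Three quarters | 0.50 + 0.25 × 0.040 = 0.510 | 0.098 |

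Type I error reaches 0.10 at p = 0.5109, that is, when (0.5109 − 0.50)/0.040 = about 27% goes uncaught.

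**Hazard shape.** With p(t) = p₅₄^((t/54)^k), k = 0.5 gives week 66 power 0.849 and week 48 type I error 0.118. With k = 1.5 they are 0.684 and 0.218.

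The effect of the change in progression definition cannot be calculated, because the documents give no rate of isolated cyst growth.

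**The case against.** The best defence is that a week 54 scan was intended. Courses 2-9 last 48 weeks, exactly four 12-week intervals from the week 6 visit, and courses 10-18 last 54 weeks, exactly three 18-week intervals. The Table 2 note also tells sites that an MRI at or after nine courses is needed. This stands to the extent that the anchor is ambiguous. A reader might infer that the protocol plainly omits the one-year scan, or that patients without a week 54 scan fail automatically. The documents support neither: one reading reaches week 54, and a later scan satisfies the note. They still leave the deciding scan without a visit or window.

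A reader might also infer that no progression rule is given for the deciding read. Section 11.1.3 does assign one by time on treatment, and weeks 66 and 72 clearly fall under the later rule. What is missing is whether progression under that rule counts against a one-year endpoint. Week 54 itself is unclear, because it lies just past 12 calendar months while the plan equates nine courses with about 12 months.

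It is fair to say that the success definition in 13.3 leans towards not counting progression first documented after course 9. The Analysis Plan dates failures by progression date, but only for PFS. The power loss is therefore the less supported of the two scenarios.

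The type I figure depends on calibration. If 50% is taken as the rate at 52.2 weeks, then 0.50^(48/52.2) = 0.529 and the type I error is about 0.136.

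One might add that a stable week 66 scan escapes central review, since 9.3.4 says for stratum 1 that "All imaging studies obtained during the first 9 courses of treatment (approximately 1 year) will be centrally reviewed by the NIC", with only smallest-measurement, response and progression scans added later. That carries little weight: the Analysis Plan uses site assessments for response and PFS and only describes discrepancies with central review.

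**Conclusion.** The point holds as a mismatch between the scan schedule and the endpoint, combined with a missing counting rule. Followed from baseline as 9.3.3 is worded, the first scheduled qualifying scan is 12 weeks (week 66) or 18 weeks (week 72) after the landmark. It is also read under a definition that can count cyst growth exempt in year 1.

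The error rates show what is at stake and do not predict the trial's operating characteristics. A reader might infer that the design is both underpowered and anti-conservative. That does not follow: the two scenarios are mutually exclusive and pull in opposite directions, and each assumes that all patients follow the baseline grid. The ceiling of 0.164 is a maximum under constant hazard only, and type I error stays below 0.10 if about three quarters of the week 48-54 progression is caught clinically. Without the mismatch the design performs as stated. This should be fixed, with medium confidence in the size of the effect, because either counting rule can push one of the two planned 10% error rates past its limit.

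**What to change.** Reconcile 9.3.3, Table 2 and its note, 11.1.3, and 13.1/13.3 so that:

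- one stratum 1 MRI, with a stated window, is tied to the end of course 9;
- the primary endpoint and the interim count are read on that scan;
- the plan states whether progression first documented on later scans counts;
- the sponsor states which of its two existing stratum 1 progression definitions applies to that read.

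How to align the scans is for the sponsor to choose. Moving the week 48 scan to week 54 would leave 54 − 36 = 18 weeks without a scheduled scan. It could also displace the 3-month confirmation of a response first seen at week 36. Section 9.3.3 covers stratum 2 as well, so the effect on its response endpoint needs checking.

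The cost is protocol wording and the re-timing of one scan. Sample size and decision boundaries do not change.
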